## 9.1.2 Definition of Serious Adverse Events

A serious adverse event is defined as an adverse event that meets at least 1 of the following serious criteria:

- Fatal
- Life threatening (places the subject at immediate risk of death)
- Requires in-patient hospitalization or prolongation of existing hospitalization
- Results in persistent or significant disability/incapacity
- Congenital anomaly/birth defect
- Other medically important serious event

An adverse event would meet the criterion of "requires hospitalization", if the event necessitated an admission to a health care facility (eg, overnight stay).

If an investigator considers an event to be clinically important, but it does not meet any of the serious criteria, the event could be classified as a serious adverse event under the criterion of "other medically important serious event". Overdose (>10% blinatumomab dose) will be classified as such. Other examples of such events could include allergic bronchospasm, convulsions, blood dyscrasias, DILI (Appendix A), or events that necessitate an emergency room visit, outpatient surgery, or urgent intervention.

The criteria for grade 4 in the CTCAE grading scale (Appendix A) differs from the regulatory criteria for serious adverse events. It is left to the investigator's judgment to report these grade 4 abnormalities as serious adverse events.

# 9.2 Safety Event Reporting Procedures

# 9.2.1 Adverse Events

# 9.2.1.1 Reporting Procedures for Adverse Events That do not Meet Serious Criteria

The investigator is responsible for ensuring that all adverse events observed by the investigator or reported by the subject that occur after enrollment through 30 days after the last dose of study treatment or the safety follow-up visit (whichever is longer) are reported using the applicable eCRF (eg, Adverse Event Summary).

The investigator must assign the following adverse event attributes:

- Adverse event diagnosis or syndrome(s), if known (if not known, signs or symptoms)
- Dates of onset and resolution (if resolved)
- Severity (and/or toxicity per protocol)

Date: 20 March 2019 Page 85 of 122

- Assessment of relatedness to blinatumomab or medical device
- Action taken

Product: Blinatumomab

If the severity of an adverse event changes from the date of onset to the date of resolution, record as a single event with the worst severity on the Adverse Event Summary eCRF.

The adverse event grading scale used will be the CTCAE. The grading scale used in this study is described in Appendix A. The investigator must assess whether the adverse event is possibly related to blinatumomab. This relationship is indicated by a "yes" or "no" response to the question: Is there a reasonable possibility that the event may have been caused by blinatumomab or other protocol-specified therapies?

The investigator must assess whether the adverse event is possibly related to any study-mandated activity (eg, administration of investigational product, protocol-required therapies, device(s) and/or procedure (including any screening procedure(s)). This relationship is indicated by a "yes" or "no" response to the question: "Is there a reasonable possibility that the event may have been caused by a study activity (eg, administration of investigational product, protocol-required therapies, device(s)), and/or procedure"?

The investigator is responsible for reviewing laboratory test results and determining whether an abnormal value in an individual study subject represents a clinically significant change from the subject's baseline values. In general, abnormal laboratory findings without clinical significance (based on the investigator's judgment) are not to be recorded as adverse events. However, laboratory value changes that require treatment or adjustment in current therapy are considered adverse events. Where applicable, clinical sequelae (not the laboratory abnormality) are to be recorded as the adverse event.

The Investigator is expected to follow reported adverse events until stabilization or reversibility.

#### 9.2.2 **Reporting Procedures for Serious Adverse Events**

The investigator is responsible for ensuring that all serious adverse events observed by the investigator or reported by the subject that occur after signing of informed consent and assent through 30 days after the last dose of study treatment or the safety follow-up visit (whichever is longer) are recorded in the subject's medical record and are submitted to Amgen/AABP.

Product: Blinatumomab

Date: 20 March 2019 Page 86 of 122

The serious adverse event must be submitted to Amgen/AABP within 24 hours following the investigator's knowledge of the event via the applicable eCRF. If the electronic data capture (EDC) system is unavailable to the site staff to report the serious adverse event, the information is to be reported to Amgen/AABP via an electronic Serious Adverse Event (eSAE) Contingency Report Form within 24 hours of the investigator's knowledge of the event. See Appendix B for a sample of the Serious Adverse Event Worksheet (eSAE) Contingency Report Form. For EDC studies where the first notification of a Serious Adverse Event is reported to Amgen/AABP via the eSAE Contingency Report Form, the data must be entered into the EDC system when the system is again available.

The investigator must assess whether the serious adverse event is possibly related to any study-mandated activity or procedure. This relationship is indicated by a "yes" or "no" response to the question: "Is there a reasonable possibility that the event may have been caused by a study activity/procedure"?

The investigator is expected to follow reported serious adverse events until stabilization or reversibility. In addition to the attributes listed in Section 9.2.1.1, the investigator must also complete the serious adverse event section of the Adverse Event Summary CRF.

New information relating to a previously reported serious adverse event must be submitted to Amgen/AABP. All new information for serious adverse events must be sent to Amgen/AABP within 24 hours following knowledge of the new information. If specifically requested, the investigator may need to provide additional follow-up information, such as discharge summaries, medical records, or extracts from the medical record. Information provided about the serious adverse event must be consistent with that recorded on the applicable eCRF (eg, Adverse Event Summary eCRF).

If a subject is permanently withdrawn from protocol-required therapies because of a serious adverse event, this information must be submitted to Amgen/AABP.

Amgen/AABP will report serious adverse events and/or suspected unexpected serious adverse reactions as required to regulatory authorities, investigators/institutions, and IRBs in compliance with all reporting requirements according to local regulations and good clinical practice.

The investigator is to notify the appropriate IRB of serious adverse events occurring at the site and other adverse event reports received from Amgen/AABP, in accordance with local procedures and statutes.

Date: 20 March 2019 Page 87 of 122

# 9.2.2.1 Reporting Serious Adverse Events After the Protocol-required Reporting Period

There is no requirement to monitor subjects for serious adverse events following the protocol-required reporting period or after end of study. However, these serious adverse events can be reported to Amgen. In some countries (eg, European Union member states), investigators are required to report serious adverse events that they become aware of after end of study. If serious adverse events are reported the investigator is to report them to Amgen within 24 hours following the investigator's knowledge of the event.

Serious adverse events reported outside of the protocol-required reporting period will be captured within the safety database as clinical trial cases for the purposes of expedited reporting.

# 9.2.2.2 Drug-induced Liver Injury Reporting & Additional Assessments Reporting

To facilitate appropriate monitoring for signals of DILI, cases of concurrent AST or ALT and TBL and/or INR elevation according to the criteria specified in Section 6.7 require the following:

The event is to be reported to Amgen/AABP as a serious adverse event within 24 hours of discovery or notification of the event (ie, before additional etiologic investigations have been concluded)

The appropriate CRF (eg, Adverse Event CRF) that captures information necessary to facilitate the evaluation of treatment-emergent liver abnormalities is to be completed and sent to the Amgen.

Other events of hepatotoxicity and potential DILI are to be reported as serious adverse events if they meet the criteria for a serious adverse event defined in Section 9.1.2.

See Appendix B for a sample of the Serious Adverse Event Worksheet /eSAE Contingency Report Form. For EDC studies where the first notification of a serious adverse event is reported to Amgen via the eSAE Contingency Report Form, the data must be entered into the EDC system when the system is again available.

The investigator must assess whether the serious adverse event is possibly related to any study-mandated activity or procedure. This relationship is indicated by a "yes" or "no" response to the question: "Is there a reasonable possibility that the event may have been caused by a study activity/procedure"?

Date: 20 March 2019

**Product: Blinatumomab** 

The investigator is expected to follow reported serious adverse events until stabilization or reversibility.

New information relating to a previously reported serious adverse event must be submitted to Amgen. All new information for serious adverse events must be sent to Amgen within 24 hours following knowledge of the new information. The investigator may be asked to provide additional follow-up information, which may include a discharge summary or extracts from the medical record. Information provided about the serious adverse event must be consistent with that recorded on the Event CRF.

#### 9.3 **Pregnancy and Lactation Reporting**

If a female subject becomes pregnant, or a male subject fathers a child, while the subject is taking blinatumomab report the pregnancy to Amgen/AABP as specified below.

In addition to reporting any pregnancies occurring during the study, investigators should monitor for pregnancies that occur after the last dose of blinatumomab through 48 hours for female subjects and for 48 hours for the female partner of male subjects.

The pregnancy should be reported to Amgen's Global Patient Safety/AABP within 24 hours of the investigator's knowledge of the event of a pregnancy. Report a pregnancy on the Pregnancy Notification Worksheet (Appendix C). The Amgen Global Patient Safety will follow-up with the investigator regarding additional information that may be requested.

If a female subject becomes pregnant during the study, the investigator should attempt to obtain information regarding the birth outcome and health of the infant. If a male subject's female partner becomes pregnant, the investigator should discuss obtaining information regarding the birth outcome and health of the infant from the pregnant partner.

If the outcome of the pregnancy meets a criterion for immediate classification as a Serious Adverse Event (eg., female subject experiences a spontaneous abortion, stillbirth, or neonatal death or there is a fetal or neonatal congenital anomaly) the investigator will report the event as a Serious Adverse Event.

If a female subject breastfeeds while taking blinatumomab, report the lactation case to Amgen/AABP as specified below.

Page 88 of 122

Date: 20 March 2019 Page 89 of 122

In addition to reporting a lactation case during the study, investigators should report lactation cases that occur after the last dose of blinatumomab through 48 hours.

Any lactation case should be reported to Amgen Global Patient Safety/AABP within 24 hours of the investigator's knowledge of event. Report a lactation case on the Lactation Notification Worksheet (Appendix D). Amgen Global Patient Safety will follow-up with the investigator regarding additional information that may be requested.

#### STATISTICAL CONSIDERATIONS 10.

- 10.1 Study Endpoints, Analysis Sets, and Covariates
- 10.1.1 **Study Endpoints**
- 10.1.1.1 **Phase 1b Primary Endpoint** 
  - Incidence of DLTs

Product: Blinatumomab

#### 10.1.1.1.1 **Phase 1b Secondary Endpoints**

- Incidence and severity of adverse events
- CR/CRh\* within first 2 cycles of treatment with blinatumomab for adults and M1 remission within the first 2 cycles of treatment with blinatumomabin pediatric subjects
- Time to hematological relapse (TTHR)
- **RFS**
- OS
- Blinatumomab PK parameters (eg, Css and clearance of blinatumomab)
- Serum cytokine concentrations
- Incidence of anti-blinatumomab antibody formation

#### 10.1.1.1.2 **Phase 1b Exploratory Endpoints**

- MRD response
- Complete MRD response

#### 10.1.1.2 **Phase 2 Primary Endpoint**

CR/CRh\* within 2 cycles of treatment with blinatumomab

#### 10.1.1.2.1 **Phase 2 Secondary Endpoints**

- TTHR
- **RFS**
- AlloHSCT after treatment with blinatumomab
- Best overall response within 2 cycles of treatment with blinatumomab
- OS
- Incidence and severity of adverse events
- 100-day mortality after alloHSCT

Date: 20 March 2019 Page 90 of 122

- Blinatumomab PK parameters (eg, Css and clearance of blinatumomab)
- Serum cytokine concentrations
- Incidence of anti-blinatumomab antibody formation

#### 10.1.1.2.2 **Phase 2 Exploratory Endpoints**

MRD response

Product: Blinatumomab

- Complete MRD response
- Peripheral blood lymphocyte subsets
- Neurological exam abnormalities and changes from baseline

#### 10.1.1.3 **Expansion Primary Endpoint**

Incidence of treatment-emergent and treatment-related adverse events

#### 10.1.1.4 **Expansion Secondary Endpoint**

CR/CRh\* within first 2 cycles of treatment with blinatumomab for adults and M1 remission within the first 2 cycles of treatment with blinatumomabin pediatric subjects

#### 10.1.1.5 **Expansion Exploratory Endpoint**

MRD remission within 2 cycles of blinatumomab

#### 10.1.2 **Analysis Sets**

The statistical analysis will be based on the following study populations: Phase 1b (dose evaluation), Phase 2 (efficacy), expansion cohort, and pooled analysis sets. Adult subjects and pediatric subjects will be summarized separately.

#### 10.1.2.1 **Full Analysis Set**

All subjects who received any infusion of blinatumomab are included in the full analysis set (FAS). This definition is in line with the intent-to-treat (ITT) principle in single-arm open-label studies. The efficacy analysis will be based on subjects from the FAS.

#### 10.1.2.2 Safety Analysis Set

For each part of the study, the safety analysis set will be the same as the FAS for that part. For the assessment of DLTs, only evaluable subjects (subjects who receive investigational product) will be included.

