### 3.4 Replacement of Subjects

Subjects enrolled in the Phase 1b part who are not evaluable for DLT as defined in Section 6.2.2 or withdraw prior to completing the DLT assessment period for any reason other than experiencing DLT(s) will be replaced. Subjects who receive ≥ 85% of the intended dose of blinatumomab but discontinue treatment for reasons other than DLT(s) prior to completion of the DLT evaluation period will be considered evaluable for safety.

Subjects enrolled in the Phase 2 part who withdraw or are removed from treatment or the study will not be replaced.

Date: 20 March 2019 Page 34 of 122

Subjects enrolled in the expansion part who withdraw or are removed from treatment or the study will not be replaced.

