## 6.2.2.3.1 Dose De-escalation Rules for Adult Subjects

During the Phase 1b part, up to 6 subjects will be enrolled in Cohort 1A and receive one to five treatment cycles of blinatumomab at a target blinatumomab dose of 9-28  $\mu$ g/day CIVI, as described in Section 6.2.1. Cohort 2 may open as soon as 5 subjects have completed the DLT observation period with no DLTs, or when 6 subjects have completed the DLT observation period with 0-1 DLT. If  $\geq$  2 subjects experience a DLT during the DLT observation period while receiving 9  $\mu$ g/day during Cohort 1A, the cohort will be closed and Cohort 1C will open at a de-escalated dose level of blinatumomab.

If ≥ 2 subjects experience a DLT during the DLT observation period while receiving 28 μg/day during Cohort 1A, the cohort will be closed and Cohort 1B will open at a de-escalated dose level of blinatumomab. Further, if 1 subject experiences a DLT at 9 μg/day and 1 subject experiences a DLT at 28 μg/day during the DLT observation period in Cohort 1A, the cohort will be closed and Cohort 1D will open at a de-escalated dose level of blinatumomab.

In Cohort 1B, up to 6 subjects will receive a target blinatumomab dose of 9-24  $\mu$ g/day CIVI. Cohort 2 may open as soon as 5 subjects have completed the DLT observation period with no DLTs, or when 6 subjects have completed the DLT observation period with 0-1 DLT. If  $\geq$  2 subjects experience a DLT during the DLT observation period during Cohort 1B, irrespective of dose level, the cohort will be closed and Cohort 1D will open at a de-escalated dose level of blinatumomab.

In Cohort 1C, up to 6 subjects will receive a target blinatumomab dose of 6-28  $\mu$ g/day CIVI. Cohort 2 may open as soon as 5 subjects have completed the DLT observation period with no DLTs, or when 6 subjects have completed the DLT observation period with 0-1 DLT. If  $\geq$  2 subjects experience a DLT during the DLT observation period during Cohort 1C, irrespective of dose level, the cohort will be closed and Cohort 1D will open at a de-escalated dose level of blinatumomab.

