## 6.2.2.4 Data Review Committee

A DRC will review safety data from each cohort in the Phase 1b part to determine if blinatumomab is safe and tolerable as defined by DLT criteria, taking into account a general benefit: risk assessment. PK data may be reviewed, if available. The DRC will meet to confirm the decision rules and recommendations summarized in Table 2 for adult subjects and Table 3 for pediatric subjects when any of the following criteria are met:

- 2 or more subjects have experienced a DLT in a cohort
- 5 or 6 subjects are enrolled in a cohort and all subjects have completed the 14-day DLT observation period

The DRC will consist of, at a minimum, members from the Amgen and Amgen Astellas Biopharma (AABP) study teams, including at least one clinician, one safety representative, and one investigator participating in the study who has recruited subjects into the cohort under review. Refer to Section 10.3.2 for more information on the scope of the DRC.

Adverse events in Appendix H and Appendix I which differ substantially in severity or tolerability compared to the currently known safety profile as determined by the DRC will be reviewed by the independent DSMB.

<sup>a Subjects who achieve a bone marrow response (blasts ≤ 5%) within 2 induction cycles of treatment may receive consolidation cycles of blinatumomab (up to a maximum of 5 total induction and consolidation cycles, or disease progression, intolerable adverse event or withdrawal of consent)

Date: 20 March 2019 Page 47 of 122

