# 10.2.1 Phase 1b Part

Given the rarity of this disease, no formal sample size estimation and statistical testing will be applied to the Phase 1b part of the study. The sample size for the dose finding phase of this study will be determined by the incidence and severity of adverse events in a rolling six Phase 1b design. For each population (adults and pediatrics subjects), a minimum of 2 and a maximum of 6 evaluable subjects will be enrolled at each dose level for determination of the dose to be selected for the Phase 2 efficacy part of the study, for a total of between 12 and 36 subjects.

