#### Phase 1b Part

No formal sample size estimation and statistical testing will be applied to the Phase 1b part of the study. The sample size for the dose finding phase of this study will be determined by the incidence and severity of adverse events in a rolling six Phase 1b design. For each population (adults and pediatric subjects), a minimum of 2 and up to 6 evaluable subjects will be enrolled at each dose level for determination of the dose to be selected for the Phase 2 efficacy part of the study, for a total of between 12 and 36 subjects.

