### **7.3 DLT Analysis Set**

For the assessment of DLTs, only DLT evaluable subjects will be included.

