#### **10.5 DLT**

Incidence rate of DLT will be summarized for adult subjects and pediatric subjects separately for Phase 1b Part of the study. The DLT summary will be based on the DLT analysis set.

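### Protocol 10.1.2.2 treats every dosed subject as evaluable for DLT, so a Phase 1b subject replaced under 3.4 can stay in the denominator and lower the reported DLT incidence

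*Protocol*

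**What the plan says.** Incidence of DLTs is the Phase 1b primary endpoint (Protocol 10.1.1.1). The places that bear on who is counted are these.

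- **Protocol 10.1.2.2** sets the safety set equal to the full analysis set, which is all dosed subjects, and then adds: "For the assessment of DLTs, only evaluable subjects (subjects who receive investigational product) will be included".
- **Protocol 3.4** replaces Phase 1b subjects "who are not evaluable for DLT as defined in Section 6.2.2 or withdraw prior to completing the DLT assessment period", unless the reason is a DLT. It also says that someone who stops early for another reason after at least 85% of the intended dose is evaluable for safety. It does not say evaluable for DLT, and does not say which dose is intended.
- **Protocol 6.2.2.3.1** (adults) lets Cohort 2 open after five completers with no DLT, or "when 6 subjects have completed the DLT observation period with 0-1 DLT".
- **Protocol 6.2.2.4** convenes the DRC when two or more subjects in a cohort have had a DLT, or when "5 or 6 subjects are enrolled in a cohort and all subjects have completed the 14-day DLT observation period".
- **SAP 7.3** says: "For the assessment of DLTs, only DLT evaluable subjects will be included". **SAP 10.5** adds: "The DLT summary will be based on the DLT analysis set".

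Section 6.2.2 gives DLT criteria, an observation period, de-escalation rules and the DRC's remit. It does not say who is evaluable. The parenthetical in 10.1.2.2 is therefore the only explicit definition in either document.

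The DLT definition in SAP Section 6 is also shorter than Protocol 6.2.2.1. It omits the DRC's power to count an Appendix H or I event of unusual severity or tolerability. It also omits the clause that makes certain prolonged discontinuations DLTs whether or not the event is in those appendices. SAP Section 11 lists neither change.

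**The concern.** A subject who stops on, say, day 6 without a DLT has not been observed through the dose step on day 8. Section 3.4 recognises that such a subject says little about tolerability and brings in another. Section 10.1.2.2 would still count that subject, as a dosed subject without a DLT. The subject is then both replaced and credited as a non-event.

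The error runs one way: each incompletely observed subject kept in the denominator makes the dose look safer. With about six subjects per dose level, one extra subject is visible in the rate. What is at stake is whether the primary endpoint is reported on the same subjects as those who supported the dose decision, and whether two programmers working from the same documents would produce the same table.

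**Working it through.** **The plan's own figure.** Protocol 10.2.1 gives 12 to 36 Phase 1b subjects. The longest de-escalation path is three cohorts in each population (1A, then 1B or 1C, then 1D; P1, then P2 or P3, then P4):

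- maximum = 3 cohorts × 6 subjects × 2 populations = 36
- minimum = 1 cohort × 6 subjects × 2 populations = 12

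The range reproduces. It allows six per cohort, with nothing added for replaced subjects.

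**One subject under each rule.** Take a dosed subject who leaves before day 14 without a DLT, with less than 85% of the dose.

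| Source | Treatment of this subject |
|---|---|
| Protocol 3.4 | Replaced |
| Protocol 6.2.2.3.1 (adults) | Not among the five or six completers |
| Protocol 10.1.2.2 | Evaluable for DLT, counted as a non-DLT |
| SAP 7.3 and 10.5 | Depends on an undefined term |

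**Effect on the reported rate.** Let x be the DLTs among six completers and k the replaced leavers. The documents give no early-leaver rate, so k is an assumption, shown from 0 to 3. The completers' rate is x/6; the rate under 10.1.2.2 is x/(6 + k).

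| DLTs (x) | k = 0 | k = 1 | k = 2 | k = 3 |
|---|---|---|---|---|
| 0 | 0% | 0% | 0% | 0% |
| 1 | 1/6 = 16.7% | 1/7 = 14.3% | 1/8 = 12.5% | 1/9 = 11.1% |
| 2 | 2/6 = 33.3% | 2/7 = 28.6% | 2/8 = 25.0% | 2/9 = 22.2% |

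With no DLT the rate stays at 0% and only the stated number of subjects grows. With k = 0 nothing changes.

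**What the 85% clause would mean.** Assume that the intended dose is the dose planned for the DLT window.

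- Adults, 14 days at 9 then 28 µg/day: 9×7 + 28×7 = 259 µg; 85% = 220.15 µg; reached at 7 + (220.15 − 63)/28 = 12.6 days.
- Pediatric, 14 days at 5 then 15 µg/m²/day: 5×7 + 15×7 = 140 µg/m²; 85% = 119; reached at 7 + (119 − 35)/15 = 12.6 days.
- Pediatric, 21 days on the 3.75, 5, 15 row of Table 5: 26.25 + 35 + 105 = 166.25 µg/m²; 85% = 141.3; reached at 14 + (141.3 − 61.25)/15 = 19.3 days.

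Read this way, the clause admits only subjects observed for nearly the whole window, so it can sensibly form part of a single definition.

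**The case against.** The best defence is that the parenthetical is a drafting slip and that the rest of the plan points the other way. The safety set is already all dosed subjects, so the word only in 10.1.2.2 would do no work if evaluable meant dosed. SAP 7.3 sets up a separate DLT set and drops the parenthetical; if it meant all dosed subjects, it would duplicate SAP 7.2. Section 3.4 is the more specific rule. This has force as to what was probably intended. It does not supply a definition: SAP 7.3 leaves the term open, and a programmer who looks it up finds only 10.1.2.2. Likewise, SAP Section 8 refers to Protocol 6.2.2 for the Phase 1b rules, which softens the shortened DLT definition in SAP Section 6 but does not correct it.

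Several stronger readings are tempting, and the documents do not support them.

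- **A wrong dose could be selected.** Table 1 counts enrolled subjects and allows one pending, and the pediatric text does not restate the completion condition. But the adult rule and the DRC trigger both require completion, and the expansion doses are already stated in 6.2.2.3.1 and 6.2.2.3.2.
- **The size limit blocks replacement.** Protocol 10.2.1 says "a minimum of 2 and a maximum of 6 evaluable subjects will be enrolled at each dose level", and SAP 3.2 says nearly the same. Replacement is blocked only if the parenthetical from 10.1.2.2 is carried into those sections. Under 3.4 a replaced subject is not evaluable and uses no place.
- **The confidence intervals shift.** Protocol 10.4.1 and SAP 10.1 specify exact intervals for efficacy incidences. DLTs are only tabulated, so no planned interval is affected.
- **The infection exemption hides deaths.** Exempting grade 3 or higher infection is a clinical choice. Infections are in Appendix H, so the DRC override and DSMB review can reach them, and fatal adverse events are tabulated separately.

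**Conclusion.** The inconsistency is real and neither document resolves it. Followed as written, 10.1.2.2 keeps a replaced subject in the denominator of the Phase 1b primary endpoint as a non-DLT. With one DLT and one replaced leaver, the reported rate drops by 16.7 − 14.3 = 2.4 percentage points; with two DLTs, by 33.3 − 28.6 = 4.7 points on the rounded figures.

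This rests on two assumptions: that at least one dosed subject left the window early without a DLT, and that the table was built on the 10.1.2.2 wording. The documents report no such subject, and if there was none, no number changes. The effect is confined to the reported DLT incidence.

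Practical reach is limited further by timing. Phase 1b summaries belong to the primary analysis (Protocol 10.3.4), and the final analysis (10.3.5) does not list DLT among the updated endpoints. The point still merits correction, because the denominator of a primary endpoint should not depend on which section is read.

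**What to change.** Delete the parenthetical in Protocol 10.1.2.2. Put one definition in Section 6.2.2, where 3.4 already sends the reader, and use it in 3.4, 10.1.2.2 and SAP 7.3. A subject is DLT-evaluable if he or she received blinatumomab and at least one of these holds:

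1. had a DLT in the window;
2. completed the 14-day window (21 days if Table 5 applied);
3. received at least 85% of the dose intended for that window.

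Subjects outside the definition are replaced, listed and kept in the safety set, but left out of the DLT denominator.

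In SAP Section 6, replace the shortened DLT definition with a cross-reference to Protocol 6.2.2.1, so that the DRC override and the clause on Appendix H and I events are not lost. List both changes in SAP Section 11.

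The cost is a few sentences and no new data. The downside is that the reported DLT rate may look slightly less favourable. Because the doses are already selected, any restated Phase 1b denominator must be labelled post hoc.
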